2.7 Study procedures

When a participant is confirmed to be SARS-CoV-2 positive all consenting household members are enrolled and randomised to the same treatment arm. All consenting household members 5 years of age and older will be given the same study treatment. Treatment is 10 days and follow up for primary outcome is 10 days. Follow up for some secondary outcomes are 28 days and outcomes related to long COVID is 6 and 12 months post randomisation.

Daily communication via SMS, online or phone will be conducted by a research team member who will be trained in standard operating procedures as per trial manual. Paediatric or adult swabs (Rhinomed) will be provided to all participants with detailed instructions for self-collection and storage until collected by a research team member. Health care provider collected PCR nasopharyngeal swabs will be collected from all participants prior to commencement of study medication and on day 3, 5 and 10 (+/- 1 day for all time points).

Phone call follow up at day 14 and 28 by a research team member will assess which participants became symptomatic after the initial treatment period and whether participants required hospitalisation during that time. Detailed medical information as to reasons for hospital admission will be sought to confirm if admission was related to COVID-19 infection or for alternative reasons. Research team members will be trained specifically in questions to ask according to trial manual, which will include an escalation process if a research team member believes that additional clinical care is required for the participant or family member.

Telemedicine follow up at day 180 +/- 10 days and day 365 +/- 10 days to ascertain any evidence of long COVID neurological symptoms.

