3.3. Definition of baseline

Baseline is defined as day 1 PCR and pre-Day 1 measures for other measures. Only measures taken prior to dispending study drug will be used as baseline measures.

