3.8. Assigning SARS CoV-2 infection status at day 1 and for all outcomes

The following algorithm will be used to determine whether a participant is regarded as positive or negative for SARS CoV-2. In general, only the health care provider collected PCR result will be used to determine infection status. The exception would be when the result was inconclusive.

SARS CoV-2 infection at the time point will be positive if the health care provider collected PCR result is "Detected" and negative if the PCR result is "Not detected".

If the result of the healthcare provider collected swab was inconclusive the following algorithm will be followed:

The result of the self-collected Rhinomed swab collected on the same date as the inconclusive healthcare provider collected swab will determine the final result. If the result of the self-collected Rhinomed swab is "Detected" the result will be positive and if the result is "Not detected" the result will be negative.

If the self-collected Rhinomed swab was also inconclusive, or was missing, the following algorithm will be followed (using the healthcare provider collected swab):

- If the inconclusive result was followed later by a "Detected" result (for example, Inconclusive on Day 3 and Detected on Day 5) then the inconclusive result will be deemed to be positive.
- If the inconclusive result was followed later by a "Not detected" result, then the inconclusive result will be deemed to be negative.
- If the inconclusive result was the last available result, then the inconclusive result will be deemed to be negative.

This algorithm will be used to determine both the primary endpoint (positive on any of Day 3, 5 or 10) and all secondary endpoints related to SARS-CoV-2 positivity.

For the primary objective only, the following two sensitivity analyses will also be done:

Sensitivity analysis 1: Only healthcare provider collected swabs will be used. If the result is inconclusive, it will be regarded as positive.

Sensitivity analysis 2: Only healthcare provider collected swabs will be used. If the result is inconclusive, it will be regarded as negative.

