3.9. Baseline covariate set

A set of covariates which will be included in models for all primary and secondary outcomes (unless specified otherwise) are: stratification factors (time from positive test to randomisation (binary)) and whether the index case is a child < 5 years(binary), participant age (continuous), inhaled steroid use at baseline (binary), days since symptom onset for index case at randomisation (continuous), whether there are children in the household (binary) and household size (continuous). This is referred to as the baseline covariate set.

Some of these covariates are correlated with each other and may also have sparse data in some of the cells, which may lead to convergence problems with the models. If that is the case, we will exclude some of the baseline covariate set until we can get a model that converges. We will first exclude the sparsest variables, and secondly exclude the variables most correlated with other variables.

We will also repeat each analysis with a model including only the two stratification variables.

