Population: Household members who tested positive for SARS CoV-2 on day 1 on a nasopharyngeal swab PCR **Treatment**: Initially randomised intervention to unfractionated intranasal heparin 1400u each nostril (as heparin solution 5,000u/ml, 140microL/actuation, TWO actuations each nostril) THREE times daily via a plastic nasal inhalator device or saline control and any subsequent deviations to the per protocol use of the intervention over 10 days

Outcome: The mean Ct value at each time point on all genes (E, N, RdRp/S gene). Ct value for the virus that was not detected will be set at the maximum number of cycles performed in the lab (40). **Summary measure**: The mean difference between arms will be reported with 95% confidence interval **Potential intercurrent events**:

Potential intercurrent events:

Index case in the household not taking study drug. This is defined as compliance <90% Participant (this household member) not taking study drug. This is defined as compliance <90% Either participant (this household member) or index case stop treatment due to adverse event Participant hospitalisation during first 10 days (removed from household) Participant received an anti-viral

Strategy for handling intercurrent event:

All intercurrent events will be handled through the treatment policy strategy, which means that the intercurrent events will be ignored.

Treatment arms will be compared using mixed effects linear regression with Ct value as the outcome, adjusting for stratification factors (time from positive test to randomisation, whether the index case is a child < 5 years), participant age, inhaled steroid use at baseline, days since symptom onset at randomisation, whether there are children in the household and household size (referred to as the defined baseline covariate set), with household as random effect to take the clustering by household into account.

Measure

1.6 Lowest Ct value amongst household members who become positive during the first 10 days

Estimand

Population: Household members who tested negative for SARS CoV-2 on day 1 on a nasopharyngeal swab PCR and subsequently become SARS CoV-2 positive during the first 10 days

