Index case in the household not taking study drug. This is defined as compliance <90% Participant (this household member) not taking study drug. This is defined as compliance <90% Either participant (this household member) or index case stop treatment due to adverse event Participant received an anti-viral

Strategy for handling intercurrent event:

All intercurrent events will be handled through the treatment policy strategy, which means that the intercurrent events will be ignored.

Treatment arms will be compared using mixed effects linear regression with maximum symptom severity as the outcome, adjusting for stratification factors (time from positive test to randomisation, whether the index case is a child < 5 years), participant age, inhaled steroid use at baseline, days since symptom onset at randomisation, whether there are children in the household and household size (referred to as the defined baseline covariate set), with household as random effect to take the clustering by household into account.

The mean difference between the treatment arms will be calculated in Stata as follows using a mixed effects GLM with random intercepts:

mixed outcome i.arm baseline_covariates || household:

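### The Measure 1.5 model for Ct on days 3, 5 and 10 leaves out the participant's own pre-drug day 1 Ct, which costs precision and leaves chance imbalance in day 1 viral load unadjusted

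*SAP*

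**What the plan says.** Measure 1.5 analyses household members who were PCR positive on day 1, index cases and contacts together. The outcome is Ct averaged over genes on days 3, 5 and 10, with this rule for negatives: "Ct value for the virus that was not detected will be set at the maximum number of cycles performed in the lab (40"). The model is fixed as follows: "Treatment arms will be compared using mixed effects linear regression with Ct value as the outcome, adjusting for stratification factors". The other terms are participant age, inhaled steroid use, days since symptom onset, children in the household and household size, plus a random intercept for household. Section 3.9 gives the same list and states that symptom duration is that of the index case: "days since symptom onset for index case at randomisation (continuous"). The only alternative in Section 3.9 is a repeat with the two stratification variables alone. Neither version contains day 1 Ct.

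The SAP nevertheless treats the day 1 PCR as a proper baseline. Section 2.7: "Health care provider collected PCR nasopharyngeal swabs will be collected from all participants prior to commencement of study medication". Section 3.3: "Baseline is defined as day 1 PCR and pre-Day 1 measures for other measures", and "Only measures taken prior to dispending study drug will be used as baseline measures". Section 2.8 records that Measures 1.5 and 1.6 are not in the protocol, so this model is fixed only in the SAP.

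Measure 4.3 (Section 6.4) has the same structure: "Treatment arms will be compared using mixed effects linear regression with maximum symptom severity as the outcome, adjusting for stratification factors". It carries the same covariates and has no baseline symptom term.

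**The concern.** When a continuous outcome is measured again after baseline, its own baseline value is usually one of the strongest predictors available. Here it is pre-drug, so adjusting for it cannot remove any treatment effect. The SAP already commits to covariate adjustment and lists several weaker candidates, but omits this one.

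The listed terms are only a partial substitute. Both illness-timing covariates, time from positive test (Section 2.5) and days since symptom onset (Section 3.9), belong to the index case. The analysed group also includes contacts already positive on day 1, and no covariate describes the stage of their infection. The household random effect does not carry a participant's own starting viral load either.

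Two things are at stake: the width of the confidence interval for Measure 1.5, and how the realised result reads if one arm happens to start with higher viral load. Bias in the usual sense is not at issue. If such an imbalance were noticed after unblinding, adding the covariate then would look selective.

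**Working it through.** **Inputs from the SAP.** Section 2.6 gives 120 households per arm, or 134 after 10% loss (120/0.9 = 133.3, rounded up), which is 268 in total, and an intracluster correlation (ICC) of 0.2 for the primary outcome. Section 2.5 gives 1:1 allocation by household. The SAP states no power, Ct standard deviation or correlation for Measure 1.5, so there is no figure of its own to reproduce.

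**Assumptions.** r is the partial correlation of day 1 Ct with follow-up Ct, given the covariates already listed; range 0.1 to 0.7. There are 1 to 2 day 1 positives per household. The ICC for Ct is 0 to 0.2.

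**Step 1, precision.** Adding the baseline value multiplies the variance of the arm difference by about 1 − r², and the interval width by √(1 − r²).

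| r | 1 − r² | variance cut | width ratio |
|---|---|---|---|
| 0.1 | 0.99 | 1% | 0.995 |
| 0.3 | 0.91 | 9% | 0.954 |
| 0.5 | 0.75 | 25% | 0.866 |
| 0.7 | 0.51 | 49% | 0.714 |

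At r = 0.5 this is equivalent to 1/0.75 − 1 = 33% more participants.

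**Step 2, check with clustering.** A random-household-intercept model was simulated with 268 households, 2 day 1 positives each, ICC 0.2 and 3000 runs. The adjusted to unadjusted variance ratios were 0.995, 0.915, 0.753 and 0.509 for the four values of r. With a true effect of zero, both models averaged within 0.002 SD of zero, so neither is biased. With 10% of day 1 values replaced by the pooled mean, the ratios were 0.993, 0.920, 0.771 and 0.548.

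**Step 3, the ceiling at 40.** Values piled up at 40 weaken the linear relation, most of all by day 10. The check used a bivariate normal with 1,000,000 draws and set the top share of the outcome to the ceiling.

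| latent r | half at ceiling: r, variance cut | three quarters at ceiling: r, variance cut |
|---|---|---|
| 0.3 | 0.257, 7% | 0.210, 4% |
| 0.5 | 0.429, 18% | 0.351, 12% |
| 0.7 | 0.600, 36% | 0.491, 24% |

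**Step 4, chance imbalance.** With H households per arm and k positives each, the SD of the day 1 Ct difference between arms, in SD units, is √(2(1 + (k − 1)·ICC)/(H·k)).

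- H = 120, k = 1: √(2/120) = 0.129, so a 95% range of ±0.25.
- H = 134, k = 2, ICC 0: √(2/268) = 0.086, so ±0.17.

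About r times the realised difference passes into the later comparison. At r = 0.5, the ends of those ranges give roughly 0.5 × 0.17 = 0.09 to 0.5 × 0.25 = 0.13 SD.

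**The case against.** The strongest reply is that nothing here is an error. The model is prespecified, adjusted for covariates and clustered by household, and its interval already allows for chance imbalance. Any omitted covariate could be criticised in the same way. This is right as far as validity goes, and the imbalance argument overlaps heavily with the precision argument. It does not explain why the SAP should forgo a baseline that it defines and collects.

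The second reply is that the size is assumed throughout, and this stands. The population mixes index cases up to 72 hours after a positive test with contacts found positive on day 1, and different phases of infection could weaken a linear relation. The 1 − r² formula also supposes that day 1 Ct predicts equally within and between households. In the extreme case where it predicts only within households (same layout, 4000 runs), overall correlations of about 0.24, 0.40 and 0.56 gave variance cuts of about 3%, 12% and 18%. The formula gives 6%, 16% and 31%. The gain shrinks but does not vanish.

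Third, the SAP establishes a day 1 PCR result but does not say outright that its Ct is kept. That also stands, and it needs confirming.

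For Measure 4.3, the maximum already excludes Day 1 and Day 2 scores. That keeps early scores out of the outcome but does not adjust for how ill participants were at entry. The day 1 diary score is not clearly usable for this: Section 3.3 admits only pre-drug measures, and Section 4.4 says the time of day of starting is unknown.

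**Conclusion.** The concern holds. The Measure 1.5 model omits the participant's own day 1 Ct, and nothing else in the SAP supplies it. The planned analysis remains valid and unbiased on average. The loss is in precision and in protection against realised imbalance. It ranges from negligible (about 1% of variance at r = 0.1) to substantial (about 49% at r = 0.7), and is smaller where many values sit at 40 or where prediction is mainly within households. The omission is certain. Its size rests on an assumed correlation, number of day 1 positives and ICC. The measure is secondary and the primary analysis is unaffected, so the change is worth making but not critical. The Measure 4.3 point is subsidiary and depends on having a symptom measure known to precede the first dose.

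**What to change.** Confirm that Ct values from the day 1 provider swab are held. Then, for each of days 3, 5 and 10, fit

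`mixed ct_dayX i.arm ct_day1 baseline_covariates || household:`

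where `ct_day1` is built with the same gene averaging and the same rule of 40 as the outcome. Tabulate it by arm with the Section 4.2 baseline characteristics.

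Some day 1 positives may lack a usable provider Ct, for example those classified under Section 3.8: "If the result of the healthcare provider collected swab was inconclusive the following algorithm will be followed". For these, impute the single mean pooled over both arms, so that nobody is dropped and the covariate stays independent of allocation.

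For Measure 4.3, add a baseline symptom covariate only if it is confirmed to precede the first dose. Otherwise use the pre-drug symptoms listed in Section 4.2, such as a count of those present. Do not use the day 1 diary score if its timing cannot be confirmed.

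Measures 1.1 to 1.3 and 1.6 can stay as written; the Measure 1.6 population is PCR negative on day 1.

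The cost is one covariate and one missing-value rule in the SAP. Measure 1.5 needs no new data collection.

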2.6 Sample size

For the primary research outcome, a sample size of 120 index cases per arm will provide 80% power. We anticipate that the attack rate for within household transmission will be approximately 85% in the control arm and 75% in the intervention arm. Under these assumptions, in a cluster randomised trial with a binary outcome, assuming an intracluster correlation coefficient of 0.2, an alpha of 0.05 (two sided), and assuming 3 additional household members (in addition to the index case) we have 80% power to detect a reduction in transmission to household contacts. The requisite sample size is then 120 index cases and 360 household contacts per arm. Allowing for 10% loss to follow-up this is increased to 134 index cases (households) per arm, approximately 536 persons per arm. We plan to enroll 268 households and approximately 1072 individuals.

If the household size is 2 additional people, rather than 3, and with all other assumptions the same, we would require 334 households and approximately 1002 individuals. The target sample size for the primary outcome is 1100 individuals enrolled.

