5. ANALYSIS OF THE PRIMARY OUTCOME(S)

5.1. Main analysis

The primary outcome will be the number (and proportion) of household members swab negative on day 1 (study timepoint called baseline) testing positive for SARS-CoV-2 by PCR on either of three routine nasopharyngeal swabs on day 3, 5 and 10 after enrolment.

Primary estimand

Population: Household members (including children < 5 years) who test negative for SARS CoV-2 on day 1 (baseline) PCR testing using the health care provider swabs

Treatment: Initially randomised intervention to unfractionated intranasal heparin 1400u each nostril (as heparin solution 5,000u/ml, 140microL/actuation, TWO actuations each nostril) THREE times daily via a plastic nasal inhalator device or saline control and any subsequent deviations to the per protocol use of the intervention over 10 days

Outcome: Testing positive for SARS-CoV-2 by PCR on any of three health care provider collected swabs at days 3, 5 and 10. The algorithm to determine SARS-CoV-2 positivity is described in detail in Section 3.8. If one of the post-baseline swabs is missing, but all observed swabs were negative, the participant will be regarded to be negative. If more than one post-baseline swab is missing and the observed swabs were all negative, the outcome will be regarded to be missing.

Summary measure: Both relative (risk ratio) and absolute differences (risk difference) in proportions will be reported with 95% confidence intervals

Potential intercurrent events:

Index case in the household not taking study drug. This is defined as compliance <90% Participant (this household member) not taking study drug. This is defined as compliance <90% Either participant (this household member) or index case stop treatment due to adverse event Participant hospitalisation during first 10 days (removed from household) Participant received an anti-viral

Strategy for handling intercurrent event:

In the primary analysis all intercurrent events will be handled through the treatment policy strategy, which means that the intercurrent events will be ignored.

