6.1 Secondary outcome 1. Efficacy of intranasal heparin to reduce SARS-CoV-2 viral shedding

To test the efficacy of intranasal heparin to reduce SARS-CoV-2 viral shedding over 10 days from day of positive swab (health professional collected swab day 3 and 5, and day 10)

Measure

1.1. Total number of index cases and household contacts combined (nasopharyngeal swab positive on day 1) who remain swab positive on day 3 according to health care provider collected swab

- 1.2. Total number of index cases and household contacts combined (nasopharyngeal swab positive on day 1) who remain swab positive on day 5 according to health care provider collected swab
- 1.3. Total number of index cases and household contacts combined (nasopharyngeal swab positive on day 1) who remain swab positive on day 10 according to health care provider collected swab

Estimand

Population: Household members who tested positive for SARS CoV-2 on day 1 on a nasopharyngeal swab PCR testing (health care provider collected swab)

Treatment: Initially randomised intervention to unfractionated intranasal heparin 1400u each nostril (as heparin solution 5,000u/ml, 140microL/actuation, TWO actuations each nostril) THREE times daily via a plastic nasal inhalator device or saline control and any subsequent deviations to the per protocol use of the intervention over 10 days

Outcome: Three different analyses will be done with 3 different outcomes

- a) Testing positive for SARS-CoV-2 by PCR on day 3 (using health care provider collected swab)
- b) Testing positive for SARS-CoV-2 by PCR on day 5 (using a health care provider collected swab)
- c) Testing positive for SARS-CoV-2 by PCR on day 10 (using a health care provider collected swab)

Summary measure: Both relative (risk ratio) and absolute differences (risk difference) in proportions will be reported with 95% confidence intervals

Potential intercurrent events:

Index case in the household not taking study drug. This is defined as compliance <90% Participant (this household member) not taking study drug. This is defined as compliance <90% Either participant (this household member) or index case stop treatment due to adverse event Participant hospitalisation during first 10 days (removed from household) Participant received an anti-viral

Strategy for handling intercurrent event:

All intercurrent events will be handled through the treatment policy strategy, which means that the intercurrent events will be ignored.

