Treatment: Initially randomised intervention to unfractionated intranasal heparin 1400u each nostril (as heparin solution 5,000u/ml, 140microL/actuation, TWO actuations each nostril) THREE times daily via a plastic nasal inhalator device or saline control and any subsequent deviations to the per protocol use of the intervention over 10 days

Outcome: The mean Ct value at each time point at or after the first positive SARS-CoV-2 test on all genes (E, N, RdRp/S gene). Ct value for the virus that was not detected will be set at the maximum number of cycles performed in the lab (40). For each participant the lowest Ct value detected at or after the first positive test will be used.

Summary measure: The mean difference between arms will be reported with 95% confidence interval

Treatment arms will be compared using mixed effects linear regression with lowest Ct value as the outcome, adjusting for the defined baseline covariate set, with household as random effect to take the clustering by household into account.

The mean difference between the treatment arms will be calculated in Stata as follows using a mixed effects GLM:

mixed outcome i.arm baseline_covariates || household:

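### Measure 1.6 compares lowest Ct only among people infected after randomisation, so its arm difference can carry selection bias in either direction if heparin changes who is infected

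*SAP*

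**What the plan says.** SAP Section 6.1 places Measure 1.6 under an efficacy objective: "To test the efficacy of intranasal heparin to reduce SARS-CoV-2 viral shedding over 10 days from day of positive swab". Its population is members negative by PCR on day 1 "and subsequently become SARS CoV-2 positive during the first 10 days". The outcome is one value per person: "For each participant the lowest Ct value detected at or after the first positive test will be used". The arms are compared by a linear mixed model, "mixed outcome i.arm baseline_covariates || household", and the result is a mean difference with a 95% confidence interval.

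The condition for entering this population is nearly the same event as the primary outcome in Section 5.1: "Testing positive for SARS-CoV-2 by PCR on any of three health care provider collected swabs at days 3, 5 and 10". Section 2.6 assumes that event occurs in "approximately 85% in the control arm and 75% in the intervention arm".

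Measures 1.1 to 1.5 use people who were positive on day 1, a status fixed before study drug. Only Measure 1.6 in this section selects on something that happens after randomisation. It has no intercurrent-event strategy, principal-stratum estimand, bounds or sensitivity analysis. Section 3.4 lists day-1 negatives as an analysis population but not the subset who later turn positive.

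**The concern.** Randomisation makes all day-1 negatives comparable between arms. It does not make those who go on to be infected comparable if treatment affects infection. Suppose heparin mainly averts infections that would have been low-load (high Ct). The infections left in the heparin arm then have lower Ct on average, and heparin looks worse on viral load without having changed it in anyone. If it mainly averts high-load infections, it looks better. Adjustment for age, steroid use, household size and the other baseline covariates may reduce the imbalance, but it does not capture exposure dose or susceptibility.

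The problem arises when the trial succeeds on its primary outcome. A successful trial could then report a false harm or a false benefit on viral load beside its main result.

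The SAP does mark non-randomised or descriptive contrasts elsewhere. Measure 2.1 states that arms will not be compared statistically, and Measures 5.1.3, 5.1.4 and 5.1.6 are set up as comparisons of exposures. Measure 1.6 carries no such label and is defined as a treatment comparison.

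**Working it through.** **Inputs from the SAP (Section 2.6).** Attack rates 85% and 75%; ICC 0.2; two-sided alpha 0.05; power 80%; 3 contacts per household; 120 households and 360 contacts per arm.

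**Inputs assumed, because the SAP gives none.** Ct SD, Ct gap between averted and remaining infections, correlation between infection propensity and viral load. All 360 contacts per arm are treated as day-1 negative.

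**1. The plan's own figure.** Pooled two-proportion formula: (1.96·√(2·0.80·0.20) + 0.842·√(0.85·0.15 + 0.75·0.25))² / 0.10² = 250 per arm. Design effect 1 + (3−1)·0.2 = 1.4, so 350 contacts, or 117 households per arm against 120 stated. Power at 360/1.4 per arm is 81.1%. With 10% loss, 120/0.9 gives 134. With 2 contacts, 250·1.2/2 = 150, /0.9 = 167 per arm, 334 in total. The design figures reproduce, so the attack rates can be carried forward.

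**2. Who enters Measure 1.6.** Placebo 0.85·360 = 306; heparin 0.75·360 = 270. If heparin only prevents infections and causes none, the share of the placebo set without a heparin counterpart is q = (0.85−0.75)/0.85 = 11.8%.

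**3. Size of the artefact for a given gap.** With no heparin effect on Ct, the absolute difference is q × (gap in mean Ct between averted and remaining infections).

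| Assumed gap (cycles) | Spurious difference (cycles) |
|---|---|
| 2 | 0.24 |
| 3 | 0.35 |
| 5 | 0.59 |
| 8 | 0.94 |

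**4. Worst case.** If the averted infections are exactly the 11.8% most extreme in one tail of a normal Ct distribution, the shift is φ(1.187)/(1−0.118) = 0.224 SD. That is 0.89, 1.12 and 1.34 cycles for an assumed SD of 4, 5 and 6. Borrowing the 1.4 design effect, the standard error is SD·√(1.4/306 + 1.4/270) = 0.099 SD, so the bound is about 2.3 standard errors.

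**5. Milder sorting.** A simulation used 120 households of 3 contacts per arm, ICC 0.2, SD 6 across all contacts, no heparin effect on Ct, and 2,000 runs per setting. The unadjusted arm means were compared with a household-clustered variance.

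| Infection rates | Correlation | Mean difference, heparin − placebo (cycles) | False-positive rate at nominal 5% |
|---|---|---|---|
| 85% vs 75% | 0 | about 0 | 5.5% |
| 85% vs 75% | 0.3 | −0.27 | 9.4% |
| 85% vs 75% | 0.5 | −0.44 | 15.6% |
| 85% vs 75% | 0.7 | −0.63 | 28.5% |
| 85% vs 75% | 1 | −0.90 | 56.7% |
| 85% vs 85% | 0.7 | 0 | 5.5% |

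The negative sign follows from the assumption that higher propensity goes with higher load. The value at correlation 1 is below the 1.34 of step 4 because SD 6 here describes all contacts, and Ct among the infected is less spread.

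**The case against.** The strongest reply has four parts.

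- **The bias is conditional.** It needs heparin to change who is infected, and infection propensity to be related to Ct. The first and last rows of the simulation table show no bias when either is absent. This stands. A reader might infer that the infected groups are necessarily non-comparable, or that the result must go against heparin. The SAP supports neither: it assumes an effect on infection but says nothing about how infection relates to Ct, so the direction is open. The mechanism is also selection on a post-randomisation event, not confounding in the strict sense.
- **The 0.22 SD is an extreme.** This stands. Varying only the SD hides the main uncertainty, which is how strongly averted infections are sorted by viral load. A reader might take about one cycle as the expected bias; it is a bound, with zero at the other end.
- **A replacement in all day-1 negatives answers another question.** Largely true. With an assumed mean Ct of 25 among the infected and no effect on their load, it would show 0.10·(40−25) = 1.5 cycles (1.0 to 2.0 for means of 30 to 20), purely from infections averted. It would also put 15% to 25% of values at the ceiling. Nor is the value 40 for people never infected already in the plan. The SAP says "Ct value for the virus that was not detected will be set at the maximum number of cycles performed in the lab (40"), but in Measure 1.6 this applies at or after a first positive. Using it more widely is an extension.
- **The stakes are limited.** True. This is one of six measures under one secondary objective, Section 2.8 declares it as an addition to the protocol, and Section 8 has no results table for it.

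None of this supplies what is missing: the SAP still specifies an arm difference with a confidence interval under an efficacy objective, without saying that it is conditional on infection.

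**Conclusion.** The point holds as a conditional one. Measure 1.6 selects on what is essentially the primary outcome, and its arm difference is open to selection bias if heparin changes who is infected and infection propensity is related to viral load. With no heparin effect on Ct, the spurious difference lies between 0 and 0.22 SD in either direction, at most about 0.9 to 1.3 cycles for an assumed SD of 4 to 6. The bound rests on the 85% and 75% rates, on heparin causing no infections, and on a normal Ct distribution. The simulated error rates come from an unadjusted comparison, so they illustrate the covariate-adjusted mixed model and do not predict its behaviour. The primary analysis and Measures 1.1 to 1.5 are not touched. The matter is of moderate weight and should be corrected because the correction is cheap.

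**What to change.** 1. In Section 6.1, Measure 1.6, state that the infected-only comparison is descriptive and conditional on infection, and is not a randomised efficacy effect. Optionally give trimming bounds, removing the excess share of infected participants from either tail of the arm with more infections.
2. Add a randomised comparison of lowest Ct over days 3, 5 and 10 in all day-1 PCR-negative members of households eligible for the primary analysis. Assign Ct 40 to those never detected, and say that this extends the existing rule. Apply the missing-swab rule of Section 5.1, so that more than one missing swab with all observed swabs negative counts as missing. Use the same mixed model, with household-clustered robust standard errors because of the ceiling at 40.
3. Report the added comparison as a combined infection and viral-load measure.

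The cost is SAP wording and one further model run. No new data are needed, and no protocol-specified measure changes, since Measure 1.6 was introduced in the SAP. The downside is that the added measure partly restates the primary outcome and does not isolate viral load among the infected; the descriptive comparison and its bounds remain for that question.
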